## **Clinical Experience**

GLA-SE has been evaluated in numerous completed or ongoing clinical trials. These trials have investigated GLA-SE formulated with antigens, including recombinant antigens, developed for vaccines against a wide variety of diseases, including leishmaniasis,[15] tuberculosis,[16,17] influenza,[18,19] schistosomiasis,[20] and malaria[21]. These clinical trials have evaluated

---

GLA-SE at 0.5, 1, 2, 2.5, 5, 10, or 20 µg dose levels. In these studies, over 1100 subjects have received at least one study injection containing GLA-SE. Safety data have not revealed any significant safety issues at any dose level tested. These studies have revealed a generally acceptable safety profile:

- Study injections are generally well tolerated;
- There have been no serious adverse events (SAEs) related to study injection;
- Injection site reactions are common and may include pain, tenderness, erythema, and induration;
- Systemic reactions may include headache, fatigue, anorexia, fever, chills, myalgia, and arthralgia;
- Transient elevations in CRP levels were noted in a study of GLA-SE administered with the Fluzone influenza vaccine; and
- Hematologic changes may occur (including decreases in hemoglobin, WBC, and neutrophils).

These reactions varied from study to study, were generally mild, resolved quickly, and are typical of vaccinations by the IM route. GLA-SE often increases the rate and severity of local and systemic reactogenicity compared to the antigen alone. This is consistent with the nonclinical animal experience and is to be expected of a potent immunostimulant.

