4.5.1. Safety Variables

Serious adverse events (SAEs) will be assessed from the time of the first study product injection through the end of the follow-up which is approximately 12 months after the last study product injection.

Solicited adverse events (AEs) will document reactogenicity events occurring from the time of each study product injection through 7 days after each study product injection. Injection site reactions of interest include pruritus, erythema, induration/swelling, pain, and tenderness. Systemic reactions of interest include fever, chills, fatigue malaise, myalgia, arthralgia, headache, nausea, and vomiting.

Unsolicited AEs will document non-serious AEs occurring from the time of each study product injection through 28 days after the study product injection.

Clinical safety laboratory AEs will be collected on the day of and prior to each study product injection, approximately 7 days after each study product injection, and approximately 28 days after each study product injection (which may also serve as the clinical safety laboratory samples for the second and/or third study product injection). Parameters to be evaluated include white blood cells (WBC), hemoglobin, platelets, alanine aminotransferase (ALT), and creatinine.

MAAEs, NOCMCs, and PIMMCs will be assessed from the time of the first study product injection through the end of the follow-up period, which is approximately 12 months after the last study product injection.

All solicited and unsolicited AEs and laboratory values are graded on a scale of 0 (absent), 1 (mild), 2 (moderate), and 3 (severe) according to toxicity grading scales ([Table 6](#), [Table 7](#)).

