9.3. Adverse Events

When calculating the incidence of adverse events (i.e., on a per subject basis), each subject will only be counted once and any repetitions of adverse events within a subject will be ignored; the denominator will be the total population size. All adverse events reported will be included in the summaries and analyses. An overall summary of adverse events is presented in [Table 18](#) along with adverse events occurring in the Safety Population ([Table 19](#)). A summary of the proportion of subjects with solicited and unsolicited AEs by treatment group will be presented in [Table 24](#).

9.3.1. **Solicited Events and Symptoms**

Systemic solicited adverse events were collected pre-vaccination, and systemic and injection site solicited adverse events were collected 30 minutes post-vaccination and then daily for 7 days after each vaccination and graded on a scale of 0 (absent), 1 (mild), 2 (moderate) and 3 (severe). Systemic events include: fever, chills, fatigue, malaise, myalgia, arthralgia, headache, nausea, and vomiting. Injection site events include: pruritus, erythema, induration/swelling, pain, and tenderness.

The proportion of subjects reporting at least one solicited adverse event will be summarized for each solicited adverse event, any systemic symptom, any injection site symptom, and any symptoms. The 95% CI calculated using Wilson score methodology from binomial distribution without continuity correction ([Table 20](#), [Table 21](#), [Table 22](#), [Table 23](#)).

For each systemic and injection site event, any systemic event, any injection site event, and any solicited event, the maximum severity over 7 days after each vaccination will be summarized for the Safety population. The number and percentage of subjects reporting each event will be summarized by the maximum severity and treatment group, separately for each vaccination and over all vaccinations. For each event the denominator is the number of subjects with non-missing data for the specific event ([Table 25](#), [Table 26](#), [Table 27](#), [Table 28](#); and [Figure 8](#), [Figure 9](#), [Figure 10](#), [Figure 11](#), [Figure 15](#), [Figure 16](#), [Figure 17](#), [Figure 18](#)).

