The number of subjects reporting a solicited adverse event will be summarized for each day post vaccination for each vaccination and for all vaccinations combined both in a summary table beginning [Table 29](#) and continuing through [Table 43](#), and graphically in a bar chart ([Figure 5](#), [Figure 6](#), [Figure 7](#), [Figure 12](#), [Figure 13](#), [Figure 14](#)). A comparison of the event rate for each treatment group between vaccination 1 and vaccination 2 and vaccination 1 and vaccination 3 will be presented ([Table 44](#)).

Solicited adverse events by subject will be presented in [Listing 10](#) and [Listing 11](#).

9.3.2. **Unsolicited Adverse Events**

The proportion of subjects reporting at least one unsolicited adverse event will be summarized by MedDRA system organ class and preferred term for each vaccination and over all vaccinations. Denominators for percentages are the number of subjects who received the vaccination being summarized. The 95% CI will be calculated using Wilson score methodology from binomial distribution without continuity correction.

Adverse events by subject will be presented in [Listing 12](#).

The following summaries for unsolicited adverse events will be presented by MedDRA system organ class, preferred term, vaccination, and treatment group:

- Subject incidence and total frequency of adverse events by treatment group and dose with 95% CI ([Table 45](#), [Table 46](#), [Table 47](#));
- Summary of severity and relationship to study product ([Table 48](#));
- Subject incidence and total frequency of related adverse events over time ([Table 49](#), [Table 50](#), [Table 51](#), [Table 52](#), [Table 53](#));
- Subject listing of non-serious adverse events of moderate or greater severity ([Table 55](#));
- Listing of other significant adverse events ([Table 56](#));
- Bar chart of non-serious related adverse events by severity and MedDRA system organ class ([Figure 19](#));

- Bar chart of non-serious related adverse events by severity ([Figure 20](#));

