Table 23: Number and Percentage of Subjects Experiencing Solicited Events with 95% Confidence Intervals by Symptom and Treatment Group – Post Any Dose

Table 24: Comparison of the Proportion of Subjects Experiencing Solicited Events by Treatment Group

[Implementation Note: Confidence intervals will be computed via the Wilson Score method.]

Symptom	Statistic	Group A: 100 µg Sm-p80 (unadjuvanted) (N=X)	Group B: 10 µg Sm-p80 + 5 µg GLA-SE (N=X)	Group C: 30 µg Sm-p80 + 5 µg GLA-SE (delayed booster) (N=X)	Group D: 30 µg Sm-p80 + 5 µg GLA-SE (N=X)	Group E: 100 µg Sm-p80 + 5 µg GLA-SE (N=X)
Any Symptom	Proportion	x.xx	x.xx	x.xx	x.xx	x.xx
	95% CI ^a (for proportion)	x.xx, x.xx	x.xx, x.xx	x.xx, x.xx	x.xx, x.xx	x.xx, x.xx
	Difference		x.xx	x.xx	x.xx	x.xx
	95% CI ^a (for difference)		x.xx, x.xx	x.xx, x.xx	x.xx, x.xx	x.xx, x.xx
Any Systemic Symptom	Proportion					
	95% CI ^a (for proportion)					
	Difference					
	95% CI ^a (for difference)					
[Systemic Symptom 1]	...					
Any Injection Site Symptom	...					
[Injection Site Symptom 1]	...					

Note: N = Number of subjects in the Safety Population who received at least one dose.

^a95% confidence intervals are from the Wilson score method without continuity correction.

Table 25: Number and Percentage of Subjects Experiencing Solicited Events by Symptom, Maximum Severity, and Treatment Group – Post Dose 1

[Implementation Note: Rows for Mild, Moderate, and Severe will only be shown if there is at least one non-zero count in that row. Confidence intervals will be computed via the Wilson Score method.]

Symptom	Severity	Group A: 100 µg Sm-p80 (unadjuvanted) (N=X)			Group B: 10 µg Sm-p80 + 5 µg GLA-SE (N=X)			Group C: 30 µg Sm-p80 + 5 µg GLA-SE (delayed booster) (N=X)			Group D: 30 µg Sm-p80 + 5 µg GLA-SE (N=X)			Group E: 100 µg Sm-p80 + 5 µg GLA-SE (N=X)			All Subjects (N = X)			
		n	%	95% CI ^a	n	%	95% CI ^a	n	%	95% CI ^a	n	%	95% CI ^a	n	%	95% CI ^a	n	%	95% CI ^a	
Any Symptom	None	X	XX	X.X, X.X	X	XX	X.X, X.X	X	XX	X.X, X.X	X	XX	X.X, X.X	X	XX	X.X, X.X	X	XX	X.X, X.X	
	Mild																			
	Moderate																			
	Severe																			
Systemic Symptoms																				
Any Systemic Symptom	None	X	XX	X.X, X.X	X	XX	X.X, X.X	X	XX	X.X, X.X	X	XX	X.X, X.X	X	XX	X.X, X.X	X	XX	X.X, X.X	
	Mild																			
	Moderate																			
	Severe																			
[Systemic Symptom 1]	None																			
	Mild																			
	Moderate																			
	Severe																			

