Table 42: Number and Percentage of Subjects Experiencing Solicited Events by Symptom, Severity, and Day Post Dosing – Group E: 100 µg Sm-p80 + 5 µg GLA-SE, Post Dose 2

Table 43: Number and Percentage of Subjects Experiencing Solicited Events by Symptom, Severity, and Day Post Dosing – Group E: 100 µg Sm-p80 + 5 µg GLA-SE, Post Dose 3

Table 44: Number and Percentage of Subjects Experiencing Solicited Events for Dose 1 Compared with Dose 2 and Dose 3 by Treatment Group

[Implementation Note: Add group name to treatment, e.g. "Group A: 100 µg Sm-p80 (unadjuvanted)."]

Treatment Group		Dose 2 – Subjects with No Symptoms	Dose 2 – Subjects with Moderate or Greater Symptoms	Dose 2 – Total Number of Subjects	Dose 3 – Subjects with No Symptoms	Dose 3 – Subjects with Moderate or Greater Symptoms	Dose 3 – Total Number of Subjects
Systemic Symptoms							
100 µg Sm-p80 (unadjuvanted)	Dose 1 Subject with No Symptoms	x (%)	x (%)	x (%)	x (%)	x (%)	x (%)
	Dose 1 Subjects with Moderate or Greater Symptoms	x (%)	x (%)	x (%)	x (%)	x (%)	x (%)
	Dose 1 Total Number of Subjects	x (%)	x (%)	x (100%)	x (%)	x (%)	x (100%)
10 µg Sm-p80 + 5 µg GLA-SE	Dose 1 Subject with No Symptoms						
	Dose 1 Subjects with Moderate or Greater Symptoms						
	Dose 1 Total Number of Subjects						
30 µg Sm-p80 + 5 µg GLA-SE	Dose 1 Subject with No Symptoms						
	Dose 1 Subjects with Moderate or Greater Symptoms						
	Dose 1 Total Number of Subjects						
30 µg Sm-p80 + 5 µg GLA-SE (delayed booster)	Dose 1 Subject with No Symptoms						

**Table 44: Number and Percentage of Subjects Experiencing Solicited Events for Dose 1 Compared with Dose 2 and Dose 3 by Treatment Group
(Continued)**

	Dose 1 Subjects with Moderate or Greater Symptoms						
	Dose 1 Total Number of Subjects						
100 µg Sm-p80 + 5 µg GLA-SE	Dose 1 Subject with No Symptoms						
	Dose 1 Subjects with Moderate or Greater Symptoms						
	Dose 1 Total Number of Subjects						
Local Symptoms							
100 µg Sm-p80 (unadjuvanted)	Dose 1 Subjects with No Symptoms	x (%)	x (%)	x (%)			
	Dose 1 Subjects with Moderate or Greater Symptoms	x (%)	x (%)	x (%)			
	Dose 1 Total Number of Subjects	x (%)	x (%)	x (100%)			
10 µg Sm-p80 + 5 µg GLA-SE	Dose 1 Subject with No Symptoms						
	Dose 1 Subjects with Moderate or Greater Symptoms						
	Dose 1 Total Number of Subjects						
30 µg Sm-p80 + 5 µg GLA-SE	Dose 1 Subject with No Symptoms						

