**Table 44: Number and Percentage of Subjects Experiencing Solicited Events for Dose 1 Compared with Dose 2 and Dose 3 by Treatment Group
(Continued)**

	Dose 1 Subjects with Moderate or Greater Symptoms						
	Dose 1 Total Number of Subjects						
30 µg Sm-p80 + 5 µg GLA-SE (delayed booster)	Dose 1 Subject with No Symptoms						
	Dose 1 Subjects with Moderate or Greater Symptoms						
	Dose 1 Total Number of Subjects						
100 µg Sm-p80 + 5 µg GLA-SE	Dose 1 Subject with No Symptoms						
	Dose 1 Subjects with Moderate or Greater Symptoms						
	Dose 1 Total Number of Subjects						

Note: Denominators for percentages are the number of subjects in the Safety Population who received both doses being compared.

Pseudo Code:

```
/*Data Format*/
```

ID	Dose1	Dose2	Dose3
A	0	1	0
B	1	1	1
C	0	0	1
D	1	1	0

Where 0 = No Symptoms and 1 = Moderate or Greater at the given dose

```
proc freq data= t56;
tables Dose1*Dose2 / out= _dose12; /*counts for dose 1 vs. dose 2*/
tables Dose1*Dose3 / out= _dose13; /*counts for dose 1 vs. dose 3*/
run;
```

14.3.1.2 Unsolicited Adverse Events**Table 45: Summary of Unsolicited Adverse Events by MedDRA System Organ Class and Preferred Term, and Treatment Group – Post Dose 1**

MedDRA System Organ Class/ Preferred Term	Group A: 100 µg Sm-p80 (unadjuvanted) (N=X)			Group B: 10 µg Sm-p80 + 5 µg GLA-SE (N=X)			Group C: 30 µg Sm-p80 + 5 µg GLA-SE (delayed booster) (N=X)			Group D: 30 µg Sm-p80 + 5 µg GLA-SE (N=X)			Group E: 100 µg Sm-p80 + 5 µg GLA-SE (N=X)			All Subjects (N=X)		
	n	%	95% CI ^a	n	%	95% CI ^a	n	%	95% CI ^a	n	%	95% CI ^a	n	%	95% CI ^a	n	%	95% CI ^a
Any SOC	x	xx	xx, xx	x	xx	xx, xx	x	xx	xx, xx	x	xx	xx, xx	x	xx	xx, xx	x	xx	xx, xx
[SOC 1]																		
[PT 1]																		
[PT 2]																		
[SOC 2]																		
[PT 1]																		
[PT 2]																		

Note: N = number of subjects in the Safety Population who received the specified dose. This table presents number and percentage of subjects. A subject is only counted once per PT/time point.

^a95% confidence intervals are from the Wilson score method without continuity correction.

Tables with similar format to Table 45:

Table 46: Summary of Unsolicited Adverse Events by MedDRA System Organ Class and Preferred Term, and Treatment Group – Post Dose 2**Table 47: Summary of Unsolicited Adverse Events by MedDRA System Organ Class and Preferred Term, and Treatment Group – Post Dose 3**

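### SAP Table 44 has no place for subjects whose worst solicited reaction is mild, although its denominator counts them

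*SAP*

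**What the plan says.** SAP 9.3.1 grades solicited events as absent, mild, moderate or severe (0 to 3). It promises "A comparison of the event rate for each treatment group between vaccination 1 and vaccination 2", and likewise between vaccinations 1 and 3, and points to Table 44 for both.

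In the Table 44 shell, each treatment group has three rows for dose 1: no symptoms, "Dose 1 Subjects with Moderate or Greater Symptoms", and a total. The columns repeat these three for dose 2 and for dose 3. The pseudo code defines the input as "Where 0 = No Symptoms and 1 = Moderate or Greater at the given dose" and cross-tabulates dose 1 with dose 2 and dose 1 with dose 3 in PROC FREQ, without a MISSING option. The footnote reads: "Denominators for percentages are the number of subjects in the Safety Population who received both doses being compared".

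Elsewhere in SAP 9.3.1 a solicited event carries no severity threshold: "The proportion of subjects reporting at least one solicited adverse event will be summarized". Tables 25-28, the maximum-severity tables, have a mild level and a rule for it: "Rows for Mild, Moderate, and Severe will only be shown if there is at least one non-zero count in that row". Table 44 has no such level and no rule.

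**The concern.** A subject whose maximum is mild at either dose belongs to the footnoted denominator but to no inner cell. The table is offered as an event-rate comparison, yet one of the three event grades is absent from it. Nothing in the SAP tells the programmer whether mild is to be coded 0, coded 1, set to missing or carried only in the totals.

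Solicited reactogenicity is a primary endpoint (Protocol 3.3.1, SAP 3.2.1). Table 44 is the tabular display that follows the same subjects from one dose to the next. A move from none to mild, or from mild to moderate or severe, is part of what such a table is for, and neither has a cell. Mild reactions are also not a remote possibility. Of earlier GLA-SE trials the protocol says: "These reactions varied from study to study, were generally mild, resolved quickly, and are typical of vaccinations by the IM route" (Protocol 2.1.4, Clinical Experience).

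**Working it through.** **Inputs**
- Severity grades: 4 (SAP 9.3.1).
- Levels in Table 44: 2, plus totals (shell and pseudo code).
- Denominator: all Safety Population subjects with both doses (Table 44 footnote).
- Group size: 9 (SAP 4.1).
- Mild rate per dose: not in the documents. Protocol 2.3.1 says there are no human safety data for these formulations. Every mild count or rate below is therefore an assumption.

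The plan states no figure to reproduce here.

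**Step 1: patterns without a cell.** Two doses with four grades give 4 × 4 = 16 patterns. Those with mild at one or both doses number 4 + 4 − 1 = 7. The other 9 fall into the 2 × 2.

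**Step 2: how likely it is that someone is unplaced.** For an assumed mild rate m per dose, the unplaced share is m if the same subjects are mild at both doses, and 1 − (1 − m)² if the doses are independent.
- m = 0.1: 0.10 to 0.19, or 0.9 to 1.7 of 9 subjects. The chance of at least one unplaced is 1 − 0.90⁹ = 61% to 1 − 0.81⁹ = 85%.
- m = 0.3: 0.30 to 0.51, or 2.7 to 4.6 of 9 subjects. The chance is 1 − 0.70⁹ = 96% to 1 − 0.49⁹ = 99.8%.

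**Step 3: what the table would print under each coding.** Take a group of 9 with k subjects mild at each dose, 1 subject moderate at both doses, and the rest with no symptoms. Unplaced subjects number k (same subjects at both doses) to 2k (no overlap). The true symptom-free share at each dose is (8 − k)/9, and the true moderate-or-greater share is 1/9 = 11%.

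| k | Unplaced | True symptom-free | Mild in totals only: inner cells sum to | Mild coded 0: symptom-free prints as | Mild missing, PROC FREQ percentages: symptom-free prints as |
|---|---|---|---|---|---|
| 1 | 1-2 | 7/9 = 78% | 8/9 to 7/9 (89% to 78%) | 8/9 = 89% | 7/8 to 6/7 (88% to 86%) |
| 2 | 2-4 | 6/9 = 67% | 7/9 to 5/9 (78% to 56%) | 8/9 = 89% | 6/7 to 4/5 (86% to 80%) |
| 3 | 3-6 | 5/9 = 56% | 6/9 to 3/9 (67% to 33%) | 8/9 = 89% | 5/6 to 2/3 (83% to 67%) |

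For k = 3:
- *Totals only.* The margins print 5/9 = 56% symptom-free and 1/9 = 11% moderate or greater, both correct. The any-grade rate, 4/9 = 44%, is found only by subtracting 5 from 9. The inner cells account for 3 to 6 of the 9 subjects.
- *Coded 0.* Three subjects with symptoms at each dose are labelled symptom-free.
- *Coded 1.* The moderate-or-greater margin becomes 4/9 = 44% instead of 11%.
- *Missing.* The base falls from 9 to between 6 and 3, and moderate or greater prints as 1/6 = 17% to 1/3 = 33%. This contradicts the footnote.

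**Step 4: the layout with a mild level.** A 3 × 3 of none, mild, and moderate or greater gives all 16 patterns a cell, so a full group sums to 9 of 9.

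**The case against.** The strongest reply is that, read literally, the table is incomplete but not wrong. The shell has explicit Total rows and columns, and the footnote fixes the percentage base. The code comments describe the PROC FREQ output as counts. The Table 16 pseudo code likewise takes counts and divides them by a separately computed total. On that reading every printed cell is correct as labelled, and mild is the remainder that is not printed. Printing 89% requires a programmer to code mild as 0 against the stated definition. Printing 67% to 83% requires using PROC FREQ's own percentages against the footnote. Any-grade rates per dose are in Tables 20-22, mild counts in Tables 25-28, and subject-level grades in Listings 10-11. Table 44 carries no test and is not in the interim package listed in SAP 6.2.

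Most of this stands, and it rules out three inferences a reader might draw. The first is that Table 44 will misstate the symptom-free share. The documents do not show this, because no coding of mild is specified. The second is that mild is the level to be expected most often. The protocol describes reactions that occurred as generally mild; it does not say that mild is more common than no reaction. Group A also receives no adjuvant. The third is that primary-endpoint data or estimates are lost, and the other tables and the listings show that they are not.

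The reply does not remove the defect. Even on its reading the inner cells fall short of a total printed as 100%, with the gap unlabelled. The comparison of any-event rates promised in SAP 9.3.1 has to be reconstructed by subtraction. If only moderate or worse reactions were of interest, the complement would be none or mild, which is not the level the shell prints.

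**Conclusion.** The point holds as a structural gap in one table. Table 44 reduces four grades to two levels that do not cover the scale, and keeps a denominator that does. Seven of 16 grade pairs have no cell. This follows from the shell, the pseudo code and the footnote, and needs no assumption.

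The numerical consequence cannot be fixed from the documents. It depends on a coding rule that the SAP does not give and on a mild rate that is unknown, so the percentages in the working are illustrations only. At best the table is incomplete; under some codings it would also be mislabelled or use the wrong base. The reach is small: one descriptive within-subject display in the final report, with the underlying data reported elsewhere. It is worth correcting because it summarizes a primary endpoint and the correction is simple.

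A separate editorial note: SAP Table 6 is titled, and cited in SAP 4.5.1, as the solicited scale. It reproduces the scales in protocol Appendix C, which itself sends the reader to protocol Tables 3-6 for solicited events. A reader might infer that reactions would be graded on the wrong scale. That is not supported, because investigators grade by protocol 8.1.2 and recorded grades are not affected.

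**What to change.** Add a mild level to the rows, columns and pseudo code of Table 44, giving none, mild, and moderate or greater at each dose. Compute all percentages on the footnoted denominator so that the cells sum to it. Collapsing to none or mild against moderate or greater would also add up, but would not give the any-event rate that SAP 9.3.1 promises.

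As an editorial correction, retitle SAP Table 6 and cite protocol Tables 3-6 for solicited events in SAP 4.5.1. The vomiting row of SAP Table 6 uses activity or episode counts (with intravenous hydration at Grade 3), while protocol Table 5 uses interference with daily activity alone. The two must be reconciled; no view is taken here on which is right.

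The cost is one table shell with its code, one table title and one cross-reference, plus the vomiting reconciliation. No new data are needed.

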Preferred Term	MedDRA System Organ Class	Group A: 100 µg Sm-p80 (unadjuvanted) (N=X)			Group B: 10 µg Sm-p80 + 5 µg GLA-SE (N=X)			Group C: 30 µg Sm-p80 + 5 µg GLA-SE (delayed booster) (N=X)			Group D: 30 µg Sm-p80 + 5 µg GLA-SE (N=X)			Group E: 100 µg Sm-p80 + 5 µg GLA-SE (N=X)			All Subjects (N=X)		
		n	%	Events	n	%	Events	n	%	Events	n	%	Events	n	%	Events	n	%	Events
Serious Adverse Events																			
All	All	x	x	x	x	x	x	x	x	x	x	x	x	x	x	x	x	x	
PT1	SOC1	x	x	x	x	x	x	x	x	x	x	x	x	x	x	x	x	x	
Etc.	Etc.																		
Other (Non-serious) Adverse Events																			
All	All	x	x	x	x	x	x	x	x	x	x	x	x	x	x	x	x	x	
PT1	SOC1	x	x	x	x	x	x	x	x	x	x	x	x	x	x	x	x	x	
Etc.	Etc.																		

Note: N = number of subjects in the Safety Population (number of subjects at risk); n = number of subjects reporting event. Events = total frequency of events reported.

14.3.1.1 Solicited Adverse Events**Table 20: Number and Percentage of Subjects Experiencing Solicited Events with 95% Confidence Intervals by Symptom and Treatment Group – Post Dose 1**

[Implementation Note: Confidence intervals will be computed via the Wilson Score method.]

Symptom	Group A: 100 µg Sm-p80 (unadjuvanted) (N=X)			Group B: 10 µg Sm-p80 + 5 µg GLA-SE (N=X)			Group C: 30 µg Sm-p80 + 5 µg GLA-SE (delayed booster) (N=X)			Group D: 30 µg Sm-p80 + 5 µg GLA-SE (delayed booster) (N=X)			Group E: 100 µg Sm-p80 + 5 µg GLA-SE (N=X)		
	n	%	95% CI ^a	n	%	95% CI ^a	n	%	95% CI ^a	n	%	95% CI ^a	n	%	95% CI ^a
Any Symptom	x	xx	x.x, x.x	x	xx	x.x, x.x	x	xx	x.x, x.x	x	xx	x.x, x.x	x	xx	x.x, x.x
Any Systemic Symptom															
[Systemic Symptom 1]															
[Systemic Symptom 2]															
Any Injection Site Symptom															
[Injection Site Symptom 1]															
[Injection Site Symptom 2]															

Note: N = Number of subjects in the Safety Population who received the specified dose; n = number of subjects reporting the specified event.

^a95% confidence intervals are from the Wilson score method without continuity correction.

Tables with similar format to [Table 20](#):

Table 21: Number and Percentage of Subjects Experiencing Solicited Events with 95% Confidence Intervals by Symptom and Treatment Group – Post Dose 2

Table 22: Number and Percentage of Subjects Experiencing Solicited Events with 95% Confidence Intervals by Symptom and Treatment Group – Post Dose 3

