[Systemic Symptom 2]	None																			

Table 25: Number and Percentage of Subjects Experiencing Solicited Events by Symptom, Maximum Severity and Treatment Group – Post Dose 1
(Continued)

Symptom	Severity	Group A: 100 µg Sm-p80 (unadjuvanted) (N=X)			Group B: 10 µg Sm-p80 + 5 µg GLA-SE (N=X)			Group C: 30 µg Sm-p80 + 5 µg GLA-SE (delayed booster) (N=X)			Group D: 30 µg Sm-p80 + 5 µg GLA-SE (N=X)			Group E: 100 µg Sm-p80 + 5 µg GLA-SE (N=X)			All Subjects (N = X)			
		n	%	95% CI ^a	n	%	95% CI ^a	n	%	95% CI ^a	n	%	95% CI ^a	n	%	95% CI ^a	n	%	95% CI ^a	
	Mild																			
	Moderate																			
	Severe																			
Injection Site Symptoms																				
Any Injection Site Symptom	None	x	xx	x.x, x.x	x	xx	x.x, x.x	x	xx	x.x, x.x	x	xx	x.x, x.x	x	xx	x.x, x.x	x	xx	x.x, x.x	
	Mild																			
	Moderate																			
	Severe																			
[Injection Site Symptom 1]	None																			
	Mild																			
	Moderate																			
	Severe																			
[Injection Site Symptom 2]	None																			
	Mild																			
	Moderate																			
	Severe																			

Table 25: Number and Percentage of Subjects Experiencing Solicited Events by Symptom, Maximum Severity and Treatment Group – Post Dose 1
(Continued)

Symptom	Severity	Group A: 100 µg Sm-p80 (unadjuvanted) (N=X)				Group B: 10 µg Sm-p80 + 5 µg GLA-SE (N=X)				Group C: 30 µg Sm-p80 + 5 µg GLA-SE (delayed booster) (N=X)				Group D: 30 µg Sm-p80 + 5 µg GLA-SE (N=X)				Group E: 100 µg Sm-p80 + 5 µg GLA-SE (N=X)				All Subjects (N = X)			
		n	%	95% CI ^a	n	%	95% CI ^a	n	%	95% CI ^a	n	%	95% CI ^a	n	%	95% CI ^a	n	%	95% CI ^a	n	%	95% CI ^a			
Note: N = Number of subjects in the Safety Population who received the specified dose. Severity is the maximum severity reported over all solicited symptoms post dosing for each subject.																									
^a 95% confidence intervals are from the Wilson score method without continuity correction.																									

Tables with similar format to [Table 25](#):**Table 26: Number and Percentage of Subjects Experiencing Solicited Events by Symptom, Maximum Severity, and Treatment Group – Post Dose 2****Table 27: Number and Percentage of Subjects Experiencing Solicited Events by Symptom, Maximum Severity, and Treatment Group – Post Dose 3****Table 28: Number and Percentage of Subjects Experiencing Solicited Events by Symptom, Maximum Severity, and Treatment Group – Post Any Dose**

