Table 48: Unsolicited Adverse Events by MedDRA System Organ Class and Preferred Term, Maximum Severity, Relationship, and Treatment Group

MedDRA System Organ Class	Preferred Term	Severity	Group A: 100 µg Sm-p80 (unadjuvanted) (N = X)				Group B: 10 µg Sm-p80 + 5 µg GLA-SE (N = X)				Group C: 30 µg Sm-p80 + 5 µg GLA-SE (delayed booster) (N = X)				Group D: 30 µg Sm-p80 + 5 µg GLA-SE (N = X)				Group E: 100 µg Sm-p80 + 5 µg GLA-SE (N = X)				All Subjects (N = X)			
			Related		Not Related		Related		Not Related		Related		Not Related		Related		Not Related		Related		Not Related		Related		Not Related	
			n	%	n	%	n	%	n	%	n	%	n	%	n	%	n	%	n	%	n	%	n	%	n	%
Any SOC	Any PT	Any Severity	X	XX	X	XX	X	XX	X	XX	X	XX	X	XX	X	XX	X	XX	X	XX	X	XX	X	XX	X	XX
		Mild																								
		Moderate																								
		Severe																								
SOC 1	PT 1	Any Severity																								
		Mild																								
		Moderate																								
		Severe																								
	PT 2	Any Severity																								
		Mild																								
		Moderate																								
		Severe																								

Note: N = Number of subjects in the Safety Population.

Table 49: Related Unsolicited Adverse Events Within 28 Days Post Dosing by MedDRA System Organ Class and Preferred Term and Dose – Group A: 100 µg Sm-p80 (unadjuvanted) (N=X)

MedDRA System Organ Class	MedDRA Preferred Term	Post Dose 1			Post Dose 2			Post Dose 3			Post Any Dose		
		n	%	Events	n	%	Events	n	%	Events	n	%	Events
Any SOC	Any PT	x	xx	x	x	xx	x	x	xx	x	x	xx	x
[SOC 1]	Any PT												
	[PT 1]												
	[PT 2]												
[SOC 2]	Any PT												
	[PT 1]												
	[PT 2]												

Note: N = Number of subjects in the Safety Population. This table presents number and percentage of subjects. For each time point, a subject is only counted once per PT.

Tables with similar format to [Table 49](#):

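### SAP Section 9.3 and the Table 49–53 shell set a different denominator from SAP Section 9.3.2 for the same tables; if they are followed and doses are missed, related unsolicited AE percentages after doses 2 and 3 print too low

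*SAP*

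**What the plan says.** The SAP gives three denominator rules for AE percentages.

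- **Section 9.3, opening paragraph.** For per-subject AE incidence, "the denominator will be the total population size".
- **Section 9.3.1, solicited events by maximum severity (Tables 25–28).** "For each event the denominator is the number of subjects with non-missing data for the specific event".
- **Section 9.3.2, unsolicited events.** "Denominators for percentages are the number of subjects who received the vaccination being summarized". This section then lists the tables it governs. Tables 45–47 are among them, and so are Tables 49–53, described as "Subject incidence and total frequency of related adverse events over time".

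The shells in SAP Appendix 1 do not all match these rules.

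- **Table 45 (format for Tables 46–47).** "Note: N = number of subjects in the Safety Population who received the specified dose". This agrees with Section 9.3.2.
- **Table 49 (format for Tables 50–53).** "Note: N = Number of subjects in the Safety Population. This table presents number and percentage of subjects". A single N stands in the title, above four column blocks: Post Dose 1, Post Dose 2, Post Dose 3 and Post Any Dose.
- **Table 20 (format for Tables 21–23).** "Note: N = Number of subjects in the Safety Population who received the specified dose; n = number of subjects reporting the specified event".
- **Table 25 (format for Tables 26–28).** "Note: N = Number of subjects in the Safety Population who received the specified dose". It does not mention the non-missing rule of Section 9.3.1.

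SAP Section 6.3.3 puts anyone with at least one dose in the Safety Population.

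**The concern.** A subject who never received dose 3 cannot have an event after dose 3. Counting that subject in the Post Dose 3 denominator lowers the percentage without adding any information about safety.

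A programmer building Tables 49–53 has Section 9.3.2 on one side. On the other are Section 9.3, the footnote and a layout with nowhere to put a per-dose N. Once a dose is missed, the two routes give different output.

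Unsolicited AEs through 28 days after each vaccination are a primary endpoint (protocol Section 3.3.1), so this is a primary safety display. Missed doses are possible: protocol Section 8.6.2 lists reasons for stopping injections in an individual, and Section 5.2.2 does not replace subjects once they have been dosed. The discontinuation criterion in protocol Section 8.6.1 needs three subjects in one group to stop because of AEs, so one or two could be lost from a group without triggering it.

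Tables 45–47 (all unsolicited AEs) and Tables 49–53 (the related subset) will be read together. If their denominators differ, the two percentages cannot be compared.

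**Working it through.** **Inputs.** Group size is 9 (protocol Section 3.1; SAP Section 4.1). Nobody is replaced after dosing (protocol Section 5.2.2). SAP Section 6.5 expects little missing data, and neither document gives a missed-dose rate. The number missing a dose, m, is therefore an assumption, taken from 0 to 3 of 9. The number of subjects with a related event, x, is taken as 1 to 3.

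**The plan's own figure.** The documents state no AE percentage. The nearest calculated figure is the chance of seeing at least one event of 20% frequency among 9 subjects: 1 − (1 − 0.20)^9 = 0.866, as printed in SAP Table 4. The sample-size table is not in question.

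**Formulas.**

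- Section 9.3 and Table 49 shell: P_shell = x / 9
- Section 9.3.2: P_dose = x / (9 − m)
- Ratio: P_shell / P_dose = (9 − m) / 9

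**Results for a Post Dose 2 or Post Dose 3 column.**

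| Missed dose (m) | Ratio | x = 1: shell vs dose-received | x = 2 | x = 3 | Shortfall, x = 1 to 3 |
|---|---|---|---|---|---|
| 0 | 1.00 | 11.1% vs 11.1% | 22.2% vs 22.2% | 33.3% vs 33.3% | 0 points |
| 1 | 0.89 | 11.1% vs 12.5% | 22.2% vs 25.0% | 33.3% vs 37.5% | 1.4 to 4.2 points |
| 2 | 0.78 | 11.1% vs 14.3% | 22.2% vs 28.6% | 33.3% vs 42.9% | 3.2 to 9.5 points |
| 3 | 0.67 | 11.1% vs 16.7% | 22.2% vs 33.3% | 33.3% vs 50.0% | 5.6 to 16.7 points |

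**Comparability.** Suppose 7 of 9 Group A subjects receive dose 3 and 3 of them have unsolicited AEs, all judged related. Table 47 prints 3/7 = 43%. Table 49, built from its shell, prints 3/9 = 33%. The same three subjects would appear under two percentages.

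**Columns not affected.** Every Safety Population subject received a first dose, so Post Dose 1 and Post Any Dose are the same under either rule. The Events column is a count with no denominator.

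**Tables 25–28.** Section 9.3.1 divides by subjects with data for the event, while the footnote defines N as recipients of the dose. The shell has rows for None, Mild, Moderate and Severe and none for missing. A recipient without data would either leave the rows short of 100% or be counted as None, unless the footnote says which denominator the percentage uses.

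**The case against.** The strongest reply is that a header N need not be a percentage denominator. SAP Section 6.1 separates them: percentages rest on non-missing observations, and tables are annotated with a population size that includes missing ones. Where a shell ties percentages to a denominator it says so, as in Tables 8, 11 and 44; Table 49 has no such statement. Section 9.3.2 already gives the right rule for these tables. On this view a competent programmer would follow it, and the footnote is merely less clear than that of Table 45.

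Part of this stands. A reader might infer that Tables 49–53 will certainly be divided by everyone ever dosed. The documents do not settle that, because Section 9.3.2 says otherwise. But the annotation reading does not remove the conflict: Section 9.3 itself names the whole population as the denominator, and the shell has no place for a per-dose N.

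Three further points limit the finding.

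- A reader might infer that reactogenicity at later doses is understated. It is not, by this route. Tables 49–53 hold related unsolicited events, while the solicited tables by dose (20–22 and 25–27) carry footnotes based on recipients of the dose.
- A reader might add that missed doses follow reactions, so later doses would look safer. Changing the denominator does not cure that: if subjects who react are withdrawn, the rate among those who go on to dose 3 is itself selected.
- Little is decided on these percentages. Halting and escalation criteria count subjects, Tables 49–53 are not in the interim output list of SAP Section 6.2, and no formal hypothesis is tested. The shells print n, and Table 8 gives doses received, so a careful reader could recompute. The uncertainty is also wide: the Wilson 95% interval is 6% to 55% for 2/9 and 8% to 64% for 2/7.

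These points bear on how much the conflict matters. They do not reconcile the instructions.

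**Conclusion.** The contradiction is real and should be removed before the tables are programmed. Section 9.3 and the Table 49 shell point to the Safety Population; Section 9.3.2, together with the sibling footnote for Tables 45–47, points to recipients of the dose.

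The numerical effect depends on two conditions: that Section 9.3 and the shell are followed, and that someone in the group misses dose 2 or 3. It is then a multiplier of (number who received the dose)/(Safety Population N): 0.89, 0.78 or 0.67 for one, two or three of nine missing. With full dosing it is nil. The missed-dose counts are assumptions.

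The finding covers related unsolicited AEs in the Post Dose 2 and Post Dose 3 columns of Tables 49–53, and the comparison of those columns with Tables 46–47. It does not show that later-dose reactogenicity is misreported. The different rules in Sections 9.3.1 and 9.3.2 are not themselves a fault, since diary items can be missing for a given event and spontaneous reports are a different kind of data. For Tables 25–28 the defect is only that the footnote does not state the denominator its own section sets.

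**What to change.** 1. In Tables 49–53, print an N for each dose column: Safety Population subjects who received that dose, and the full Safety Population N for Post Any Dose. Reword the footnote to match.
2. In Section 9.3, limit the whole-population denominator to any-dose summaries.
3. In the Table 25–28 footnote, state that percentages use the non-missing denominator already set in Section 9.3.1. No new rule for solicited data is needed.

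The cost is one sentence in Section 9.3, two footnotes (each carried to its sibling tables) and a column-header change in one shell. No data collection, sample size or trial conduct is affected.
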